## Introduction

*Helicobacter pylori* (*H. pylori*) infect more than 50% of humans globally. It is the principal cause of chronic gastritis, gastric ulcer, duodenal ulcer, gastric adenocarcinoma and gastric mucosa-associated lymphoid tissue lymphoma (MALToma) [1,2]. In most international guidelines [3-6], standard triple therapy consisting of a proton-pump inhibitor (PPI), clarithromycin and amoxicillin (or metronidazole) for 7 to 14 days is recommended as the choice of treatment for first-line therapy of *H pylori* infection, especially in areas of low clarithromycin resistance (< 15%). Recently, the eradication rates of standard triple therapy have declined to less than 80% in many countries, largely owing to emerging organism resistances [7-10]. Some European studies even reported very poor treatment outcomes of the standard therapy with failure rates of 25-60% [11-13]. Several strategies including sequential therapy, concomitant therapy and hybrid therapy have therefore been proposed to increase the eradication rate [14-16].

Concomitant therapy is another novel regimen proven successful in the presence of clarithromycin resistance [15]. It is a 4-drug regimen containing a PPI (standard dose, b.i.d.), clarithromycin (500 mg, b.i.d.), amoxicillin (1 g, b.i.d.) and metronidazole (500 mg, b.i.d.)

which are all given for the entire duration of therapy. This therapy is superior to standard triple therapy for *H pylori* eradication [17]. It is also less complex than sequential therapy as this regimen does not involve changing drugs halfway through. A head-to-head non-inferiority trial of 10-day sequential and 10-day concomitant therapy showed they were equivalent (93.1% vs 93.0% by per-protocol analysis) [18].

Recently, we have developed a new anti-*H pylori* regimen — hybrid therapy , which consists of a dual therapy with a PPI (standard dose, b.i.d.) and amoxicillin (1 g, b.i.d.) for 7 days followed by a quadruple regimen with a PPI (standard dose, b.i.d.), amoxicillin (1 g, b.i.d.), clarithromycin (500 mg, b.i.d.) and metronidazole (500 mg, b.i.d.) for 7 days [16]. The novel therapy provided excellent eradication rates of 99% and 97% according to per-protocol and intention-to-treat analysis [16]. Several randomized controlled trials subsequently demonstrated that hybrid regimens were comparable with or more effective than sequential regimens [19-22]. It is important to note that the new therapy has a high efficacy in the treatment of *H pylori* strains harboring dual resistance to clarithromycin and metronidazole. Several studies have shown that sequential therapy is ineffective to clear *H pylori* with dual resistance [14]. The prolonging treatment duration of amoxicillin to 14 days in hybrid therapy might account for the higher eradication rate in the face of *H pylori* stains with dual resistance to clarithromycin and metronidazole. A study from Italy [20] which compared markedly different durations of therapy (14-day hybrid therapy vs 5-day concomitant therapy) showed that 14-day hybrid therapy was superior by PP analysis (95.7% vs 85.1%). However, another

randomized controlled trial showed comparable eradication efficacy between hybrid and concomitant therapies [23]. The study also showed that there was a borderline significant trend toward higher compliance with hybrid therapy compared with concomitant therapy (99% vs 95%) [23]. Many expert recommendations therefore proposed hybrid therapy as a treatment option for *H pylori* in areas with moderate or high clarithromycin resistance [24-27].

Switching drugs halfway through the course increases the complexity of an anti-*H pylori* regimen. Reversing the sequence of drug administration (a quadruple regimen followed by a dual regimen) simplifies hybrid therapy and make it become a one-step two-phase therapy. We recently conducted a multi-center, randomized controlled trial to compare the efficacies of reverse hybrid therapy and standard triple therapy [28]. The data indicated that reverse hybrid therapy achieved a higher eradication rate than standard triple therapy (95.5% vs 88.6%) by ITT analysis.

Currently, whether reverse hybrid therapy is superior to concomitant therapy in *H pylori* eradication remains unanswered. Theoretically, the ideal treatment for *H pylori* infection should be a cheap, highly effective, and well-tolerated therapy. Since the pharmaceutical cost of 14-day reverse hybrid therapy is cheaper than 14-day concomitant therapy, the former would be a better choice than the latter for *H pylori* eradication if its eradication rate is superior or non-inferior to that of concomitant therapy. We hence conduct the randomized controlled trial are (1) to compare the efficacies of 14-day reverse hybrid therapy and 14-day concomitant therapy, (2) to investigate the host and bacterial factors predicting the treatment outcomes of the two eradication regimens.

## PATIENTS & METHODS

### Study population

The open-labeled trial is conducted at the Kaohsiung Veterans General Hospital and Kaohsiung Medical University Hospital in Taiwan in accordance with the principles of good clinical practice from the Declaration of Helsinki. The study protocol will be approved by the Ethics Committees of the Kaohsiung Veterans General Hospital and the Kaohsiung Medical University Hospital. All patients give written informed consent before participating in the study.

We will recruit 248 patients to the study if they meet the following criteria: they are adult patients aged  $\geq 20$  years and have *H pylori* infection. The exclusion criteria include The exclusion criteria include (1) previous *H pylori*-eradication therapy, (2) patient with allergic history to the medications used, (3) patients with previous gastric surgery, (4) coexistence of serious concomitant illness (for example, decompensated liver cirrhosis, uremia), and (5) pregnant women.

### ***Randomization and treatment***

This is a randomized controlled trial. Eligible *H. pylori*-infected subjects are randomly assigned to a 14-day reverse hybrid therapy (a 7-day quadruple regimen with dexlansoprazole MR 60 mg once daily, amoxicillin 1 g twice daily, clarithromycin 500 mg twice daily, and metronidazole 500 mg twice daily, followed by a 7-day dual regimen with dexlansoprazole 60 mg once daily and amoxicillin 1 g twice daily) or a 14-day concomitant therapy (dexlansoprazole

MR 60 mg once daily, amoxicillin 1 g twice daily, clarithromycin 500 mg twice daily, and metronidazole 500 mg twice daily for 14 days). All drugs are taken one hour before breakfast or dinner. Patients with peptic ulcers in initial endoscopy receive an additional 4-week dexlansoprazole MR therapy (60 mg orally once daily), while patients with symptomatic gastritis only take additional four-weeks of antacid.

On recruitment, patients are requested to complete a standard record for a complete medical history and demographic data. Additionally, blood sampling for genotyping of *CYP2C19* is carried out. To assess eradication efficacy and status of ulcer healing, repeated endoscopy with rapid urease test, histological examination and culture is performed for peptic ulcer patients at the sixth week after the end of anti- *H. pylori* therapy. Urea breath test is conducted to assess *H. pylori* status in the subjects with gastritis and in peptic ulcer subjects who refuse follow-up endoscopy. Eradication is defined as (1) negative results of both rapid urease test and histology, or (2) a negative result of urea breath test.

Finally, the eradication rates by both intention-to-treat and per-protocol analyses, adverse events and compliance will be compared between groups by chi-square test, and the host and bacterial factors influencing the efficacy of eradication therapy are assessed by multivariate analysis.

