### ***Statistical analysis***

The primary outcome variable is eradication rate. The secondary outcome variables are the rate

of adverse events and compliance. Chi-square test with or without Yates correction for continuity and Fisher's exact test are used when appropriate to compare the major outcomes between groups using the SPSS program (version 10.1, Chicago, Illinois, USA). A *P* value less than 0.05 is considered statistically significant.

Eradication rates are evaluated by ITT and per-protocol (PP) analyses. ITT analysis includes all randomized patients who have taken at least one dose of study medication. Patients whose infection status is unknown following treatment are considered treatment failures for the purposes of ITT analysis. The PP analysis excludes the patients with unknown *H. pylori* status following therapy and those with major protocol violations.

To determine the independent factors affecting the treatment response, Host and bacterial parameters are analyzed by univariate analysis. These variables include the following: age (<60 or  $\geq$ 60 years), gender, history of smoking, history of alcohol consumption (<80 g/day or  $\geq$ 80 g/day), ingestion of coffee (<1 cup/day or  $\geq$ 1 cup/day), ingestion of tea ((<1 cup/day or  $\geq$ 1 cup/day), coexistence of a systemic disease (yes or no), previous history of peptic ulcer disease, endoscopic appearance (ulcer or gastritis), CYP2C19 polymorphism, drug compliance (good or poor), and antibiotic susceptibility. Those variables found to be significant by univariate analysis are subsequently assessed by a stepwise logistic regression method to identify independent factors for eradication outcome.

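### Culture is taken at the week-6 endoscopy to assess eradication but is not in the endoscopic criterion, so a patient positive on culture alone counts as eradicated (minor)

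*Combined protocol and SAP*

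**What the plan says.** All the relevant text is in the combined protocol and SAP.

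- **Tests and purpose (Randomization and treatment).** "To assess eradication efficacy and status of ulcer healing, repeated endoscopy with rapid urease test, histological examination and culture is performed" in patients with peptic ulcer, "at the sixth week after the end of anti- *H. pylori* therapy".
- **Breath-test route (same section).** The urea breath test is used "in the subjects with gastritis and in peptic ulcer subjects who refuse follow-up endoscopy".
- **Definition (same section).** "Eradication is defined as (1) negative results of both rapid urease test and histology, or (2) a negative result of urea breath test".
- **Role of the endpoint (Statistical analysis).** "The primary outcome variable is eradication rate".
- **Only rule for problem results (Statistical analysis).** "Patients whose infection status is unknown following treatment are considered treatment failures for the purposes of ITT analysis". The PP set drops patients of unknown status and those with major violations.

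Neither section says how a positive follow-up culture is used, and there is no rule for tests that disagree.

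**The concern.** On the endoscopy route three tests are taken, with eradication among the stated purposes, but only two decide the outcome. The word for two in criterion (1) makes it an explicit two-test rule, so culture cannot be read into it. A patient from whom the organism is grown six weeks after treatment can therefore be recorded as cured.

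This touches the primary outcome. It also touches the second aim, because the same success/failure variable is the dependent variable in the analysis of host and bacterial predictors. The trial is open-label, so the scoring of a discordant result should be settled in advance and not case by case.

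**Working it through.** The plan gives no figure on this point to reproduce. The check is a reading of the rules, followed by a calculation for scale.

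**Step 1. Apply the stated rule to each pattern of results on the endoscopy route.**

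| Urease test | Histology | Culture | Plan's rule | Rule with culture added |
|---|---|---|---|---|
| negative | negative | negative | eradicated | eradicated |
| negative | negative | failed or missing | eradicated | eradicated |
| negative | negative | **positive** | **eradicated** | **not eradicated** |
| either or both positive | | any | not eradicated | not eradicated |

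Only the third row changes. A culture-positive patient with another positive test is already a failure. Patients assessed by breath test are unaffected.

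**Step 2. Look for another rule that would catch the third row.**

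- ITT: failure is imputed only when status is unknown. This patient's status is defined by criterion (1), so the patient is a success.
- PP: exclusion needs unknown status or a major violation. Neither follows from a positive culture, so the patient stays in and is a success.

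**Step 3. Look for another stated role for the follow-up culture.** The Abstract places antibiotic susceptibility testing at recruitment. No section gives the week-6 culture a separate purpose.

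**Step 4. Scale.** Inputs: N = 248 (Study population). Allocation of 1:1 is assumed because no ratio is stated. The number per arm is 248/2 = 124. With k patients positive on culture alone in an arm, its ITT rate under the plan exceeds the rate under the amended rule by k/124:

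- k = 0: 0 points
- k = 1: 1/124 = 0.8 points
- k = 2: 2/124 = 1.6 points
- k = 3: 3/124 = 2.4 points

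The between-arm difference shifts by (k1 − k2)/124. This is 0 when the counts are equal and 2.4 points for 3 against 0. The values of k are illustrative. The documents give neither the share of patients having repeat endoscopy nor the frequency of culture-only positives, so 2.4 points is not a bound.

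**Step 5. Scale against the number of failures.** The Introduction cites ITT eradication rates of 95.5% for reverse hybrid therapy and 97% for hybrid therapy. If an arm performed in that range, failures among 124 would number 0.045 × 124 = 5.6 down to 0.03 × 124 = 3.7, or about 4 to 6. One reclassified patient would change a count of that size noticeably, which matters most for the predictor analysis.

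**The case against.** The strongest reply is that the rule is complete and unambiguous. Any two readers would classify every patient alike, and it applies equally to both arms. Taking a test that does not enter the endpoint is not in itself a fault. The purpose clause introduces the endoscopy as a whole, including ulcer healing, and need not give each biopsy test a role in the endpoint. Culture might be meant for susceptibility testing of failures. The documents give no accuracy figures for any test, so a lone positive culture is not shown to be right and two negatives wrong. Finally, adding culture makes endoscopy patients pass three tests and breath-test patients one, while ulcer versus gastritis is itself a planned predictor.

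Much of this stands as a limit on the size of the point. The rule is not contradictory, the frequency is unknown, and no effect on the between-arm test is shown. The direction (rates raised or unchanged) holds relative to a definition that treats growth of the organism as persistent infection. The uneven ascertainment is a real cost.

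It does not remove the point. Growth of the organism is direct evidence that it is still present, whereas the other two tests being negative is only failure to detect it. The susceptibility explanation is possible but appears nowhere in the documents. Nor does the plan give a reason for setting aside a positive result from a test taken partly to assess eradication.

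**Conclusion.** The concern holds, as a minor one. For one pattern (endoscopy route, urease test and histology negative, culture positive) the plan scores a patient with cultured *H. pylori* as eradicated in ITT and, absent a major violation, in PP. Each such patient is worth 0.8 percentage points on an arm's ITT rate if allocation is 1:1 and all 248 patients enter the ITT set. That set requires at least one dose, so the denominator could be slightly smaller. The number of such patients is unknown and may be zero. The effect on the between-arm difference is unknown and probably small, and no effect on the P value is claimed.

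**What to change.** Amend criterion (1) to require a negative rapid urease test, negative histology and no growth of *H. pylori* on follow-up culture. State that a failed or missing culture counts as not positive, so that no patient's status becomes unknown because of it. Apply the rule identically in both arms, and report by arm how many patients had culture as their only positive test.

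If the sponsor prefers the two-test rule, the plan should say that follow-up culture does not contribute to the endpoint and why. That settles the ambiguity about its role but still scores the culture-only positive as a success, so the count by arm should be reported in that case too.

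The cost is one clause. The culture is already planned, so there is no added procedure. The eradication rate may be marginally lower, and ulcer and gastritis patients will be judged slightly less alike, which should be borne in mind when endoscopic appearance is read as a predictor.

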### ***Statistical analysis***

The primary outcome variable is eradication rate. The secondary outcome variables are the rate

of adverse events and compliance. Chi-square test with or without Yates correction for continuity and Fisher's exact test are used when appropriate to compare the major outcomes between groups using the SPSS program (version 10.1, Chicago, Illinois, USA). A *P* value less than 0.05 is considered statistically significant.

Eradication rates are evaluated by ITT and per-protocol (PP) analyses. ITT analysis includes all randomized patients who have taken at least one dose of study medication. Patients whose infection status is unknown following treatment are considered treatment failures for the purposes of ITT analysis. The PP analysis excludes the patients with unknown *H. pylori* status following therapy and those with major protocol violations.

To determine the independent factors affecting the treatment response, Host and bacterial parameters are analyzed by univariate analysis. These variables include the following: age (<60 or  $\geq$ 60 years), gender, history of smoking, history of alcohol consumption (<80 g/day or  $\geq$ 80 g/day), ingestion of coffee (<1 cup/day or  $\geq$ 1 cup/day), ingestion of tea ((<1 cup/day or  $\geq$ 1 cup/day), coexistence of a systemic disease (yes or no), previous history of peptic ulcer disease, endoscopic appearance (ulcer or gastritis), CYP2C19 polymorphism, drug compliance (good or poor), and antibiotic susceptibility. Those variables found to be significant by univariate analysis are subsequently assessed by a stepwise logistic regression method to identify independent factors for eradication outcome.

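### Stratifying the primary comparison by baseline diagnosis (ulcer or gastritis) would be a small, free improvement on a valid unadjusted chi-square test

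*Combined protocol and SAP*

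**What the plan says.** The Statistical analysis section states "The primary outcome variable is eradication rate". It then says that chi-square tests, with or without Yates correction, and Fisher's exact test "are used when appropriate to compare the major outcomes between groups". No stratum, covariate or centre term is named. The last paragraph of Randomization and treatment repeats the chi-square comparison for the intention-to-treat and per-protocol rates.

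Randomization and treatment makes two things depend on the initial endoscopy:
- **Acid suppression after treatment.** Ulcer patients "receive an additional 4-week dexlansoprazole MR therapy"; those with symptomatic gastritis take antacid for the same period.
- **Test of cure.** Ulcer patients have a repeat endoscopy and count as eradicated if rapid urease test and histology are both negative. For gastritis patients, "Urea breath test is conducted to assess" infection status, and one negative result is enough. Ulcer patients who refuse the second endoscopy also have the breath test.

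Endoscopic appearance (ulcer versus gastritis) is one of the candidate predictors in the univariate-then-stepwise analysis. That list contains neither treatment arm nor centre, so it yields no planned adjusted comparison of the arms. The trial is open-label at two hospitals, and no randomisation method or stratification factor is stated.

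**The concern.** Diagnosis is known at baseline, and the plan itself treats it as possibly prognostic. It also governs how the endpoint is usually measured and what the patient takes in the weeks before measurement. If measured eradication differs between ulcer and gastritis patients, for whatever reason, a chance difference between the arms in ulcer share moves the crude arm difference in that particular trial. Nothing in the documents shows that randomisation balances diagnosis, and no other planned analysis adjusts for it. What is at stake is how accurate the estimate is given the imbalance that actually occurs, plus a little precision.

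**Working it through.** **Inputs from the documents.** The total is 248 (Study population), given without power, effect size or margin, so there is no derivation to reproduce; it is used here only as a total. The significance level is 0.05 (Statistical analysis).

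**Assumptions.** Equal allocation, so n = 124 per arm. Ulcer share q = 30% or 50%. Gap g in measured eradication between diagnoses = 5 or 10 points. Eradication is 93% in both arms, close to the per-protocol rate that the Introduction cites for 10-day concomitant therapy. The documents give no ulcer share and no rate by diagnosis.

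**Step 1: chance imbalance in ulcer share.** SD = sqrt(2q(1-q)/n).
- q = 0.3: sqrt(0.42/124) = 5.82 points; × 1.96 = 11.4 points.
- q = 0.5: sqrt(0.50/124) = 6.35 points; × 1.96 = 12.4 points.

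**Step 2: shift in the crude difference at that limit.** Shift = imbalance × gap.

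| Ulcer share | g = 5 points | g = 10 points |
|---|---|---|
| 30% | 0.114 × 5 = 0.57 | 0.114 × 10 = 1.14 |
| 50% | 0.1245 × 5 = 0.62 | 0.1245 × 10 = 1.24 |

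At a typical imbalance of one SD, the shift is 0.0582 × 5 = 0.29 to 0.0635 × 10 = 0.64 points. With a gap of only 3 points, the shift at the 95% limit is 0.3-0.4.

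**Step 3: yardstick.** The standard error of the crude difference is sqrt(2 × 0.93 × 0.07/124) = sqrt(0.00105) = 3.24 points. The shifts in the table are therefore 0.57/3.24 = 0.18 to 1.24/3.24 = 0.38 standard errors.

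**Step 4: precision gained.** Stratifying removes approximately the variance 2q(1-q)g²/n.
- q = 0.5, g = 0.05: sqrt(0.00105 - 0.0000101) = 3.22 points.
- q = 0.3, g = 0.10: sqrt(0.00105 - 0.0000339) = 3.19 points.
- q = 0.5, g = 0.10: sqrt(0.00105 - 0.0000403) = 3.18 points.

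Simulation agrees. The SD goes from about 3.25 to 3.26 if diagnosis has no effect, and from 3.24 to 3.18-3.19 with a 10-point gap.

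**Step 5: operating characteristics.** These come from 200,000 simulated trials per scenario, with half the patients having ulcer.
- Type I error at 93% in both arms, 5-point gap: 4.8% crude, 4.9% stratified.
- Power at 95.5% vs 88.6% (the rates cited from the trial of reverse hybrid against triple therapy, used for illustration): 52.4% vs 52.8% with a 5-point gap, and 52.5% vs 53.5% with an 8-point gap.
- With a 5-point gap, the two tests disagree on significance in about 1.0% of null trials and 3.4% of trials at 95.5% vs 88.6%.
- In the roughly 2.4% of trials where the imbalance reaches 12.4 points in one direction, the crude difference under the null is off by 0.73 points on average (5-point gap) or 1.12 (8-point gap). The stratified estimate is off by 0.01 and 0.07.

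**The case against.** The strongest reply is that nothing here is wrong. The diagnosis-dependent rules are the same in both arms, so under randomisation the crude test is valid, and chance imbalance in ulcer share is already part of its standard error. The gain in power is about one percentage point or less, the stratum gap is assumed, and the documents give no centre split or rates by centre. All of this stands. It limits the point to an optional-looking refinement, but does not argue against a change that costs essentially nothing.

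A reader might infer more, in three ways that the documents do not support.
- *That the result is biased.* It is not. Both estimators are unbiased over randomisation; only accuracy given the realised imbalance differs.
- *That diagnosis determines the test of cure, so that stratifying compares like with like within each test method.* Ulcer patients who refuse endoscopy have a breath test, so the ulcer stratum mixes both methods.
- *That the shift is large beside 95.5% - 93.0% = 2.5 points.* Those cited rates come from different trials, one intention-to-treat with 14-day reverse hybrid therapy and the other per-protocol with a 10-day concomitant regimen. Their difference is not an expected effect in this trial.

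Sparse data is a fair worry if centre is added. At 93% eradication, 248 × 0.07 gives about 17 failures. With eight equal arm-by-diagnosis-by-centre cells of 31, the chance that at least one has no failures is 1 - (1 - 0.93^31)^8, or about 59%. The Mantel-Haenszel method tolerates such cells, so this is a reason not to add a vague rule for collapsing strata rather than a reason not to stratify.

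**Conclusion.** The point holds as a small improvement, not as an error. The unadjusted primary comparison is valid. Given 124 per arm, 30-50% ulcer and a 5-10 point gap between diagnoses, none of which the documents state, stratifying removes a shift of about 0.6-1.2 points at the 95% limit of imbalance, against a standard error of about 3.2. If diagnosis turns out not to matter, the cost is about 0.01 points of SD.

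Stratifying does not deal with a separate risk. In an open-label trial, refusal of the second endoscopy could differ by arm. That would not be chance imbalance, and a baseline stratum would not correct it.

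**What to change.** In Statistical analysis:
- Pre-specify, for the primary comparison, a Mantel-Haenszel risk difference with 95% CI and a Cochran-Mantel-Haenszel test, stratified by baseline endoscopic diagnosis. Keep the crude chi-square as supportive.
- Stratify by the initial diagnosis, not by the test performed. The test is partly chosen after randomisation, and a patient with no follow-up test would have no stratum.
- Add centre as a further stratum only if randomisation was stratified by centre, or as a sensitivity analysis. State the randomisation method so that this can be settled. No rule for collapsing sparse strata is needed.
- Report the test-of-cure route (endoscopic, breath test, none) by arm and diagnosis, including refusals of repeat endoscopy.

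The cost is a few sentences and one table, with no new data and no more patients. The risk difference is a weighted average of the stratum differences, with weights n1·n0/(n1+n0) where n1 and n0 are the two arms' numbers in the stratum, so it can be computed from the stratum tables in any software.

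### Age enters the predictor analysis only as under 60 versus 60 or over; if its effect is roughly linear, the split loses about 36–51% of the information on age, with few failures expected

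*Combined protocol and SAP*

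**What the plan says.** All of this is in the combined protocol and SAP.

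- **Coding of age.** In the Statistical analysis section the list of candidate predictors opens with "These variables include the following: age (<60 or"; the second group is 60 years or more. No other form of age is mentioned, and no reason is given for the cut.
- **Model building.** "Those variables found to be significant by univariate analysis are subsequently assessed by a stepwise logistic regression method". Age therefore has to pass the univariate screen in its two-group form before it can reach the multivariable model.
- **Significance level.** A "value less than 0.05 is considered statistically significant". Sidedness is not stated.
- **Data on age.** The Study population section says of eligible patients that "they are adult patients aged" 20 years or more, and the Randomization and treatment section has demographic data taken at recruitment. Age in years must therefore be known for everyone.
- **Size.** "We will recruit 248 patients to the study". The documents give no expected number of failures and no mean, spread or upper limit for age.

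**The concern.** Identifying predictors is one of the trial's two stated aims. Its precision is governed by the number of treatment failures, which will be small if both regimens work as well as the cited studies suggest. A two-group age variable treats patients of 59 and 61 as different and patients of 21 and 59 as the same. If the risk of failure changes gradually with age, that discards information the trial already holds, and a weakened age variable is more likely to fall at the screen. A continuous linear term costs one degree of freedom, the same as the split.

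**Working it through.** **1. Expected failures.** The documents state none, so there is no planned figure to reproduce. Inputs: 248 patients, taken as 124 per arm (equal allocation is assumed; no ratio is given), and eradication rates cited in the Introduction.

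- Reverse hybrid therapy 95.5% (ITT): 124 × 0.045 = 5.6.
- Concomitant therapy 93.0% (per protocol, 10-day regimen, used as a proxy): 124 × 0.070 = 8.7.
- Total: 5.6 + 8.7 = 14.3, or about 14.
- Range: 97% in both arms (the ITT rate cited for hybrid therapy) gives 248 × 0.03 = 7.4; 93% in both arms gives 248 × 0.07 = 17.4.

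The central figure mixes an ITT rate with a per-protocol rate from a shorter regimen, so the range matters more than the 14. Patients of unknown status, who count as failures in the ITT analysis, would come on top.

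**2. Information kept by the split.** For a linear effect, the efficiency of a two-group version relative to the continuous variable is the squared correlation between the two. For a normal variable with share p above the cut and standardised cut-point c, this is φ(c)² / [p(1 − p)].

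| Share aged ≥60 (assumed) | Efficiency | Loss | 14 failures are worth about |
|---|---|---|---|
| 50% | 0.64 | 36% | 8.9 |
| 40% | 0.62 | 38% | 8.7 |
| 30% | 0.58 | 42% | 8.1 |
| 20% | 0.49 | 51% | 6.9 |
| 10% | 0.34 | 66% | 4.8 |

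The last column is 14 × efficiency (unrounded). Example at 50%: c = 0, φ(0) = 0.399, and 0.399² / 0.25 = 0.64. A uniform age distribution from 20 to 80 gives a loss of 33%. The 36–51% range thus corresponds to about 20–50% of patients being 60 or over; with fewer older patients the loss exceeds a half.

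**3. Effect on power.** Simulation of 248 patients with 14 expected failures, age with mean 53 and SD 13 (both assumed; about 30% are then ≥60), a linear effect on the logit, a two-sided 0.05 score test and 4,000 runs per row. The odds ratio per 10 years is the odds ratio per SD raised to the power 10/13.

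| OR per SD | OR per 10 years | Power, continuous | Power, split at 60 |
|---|---|---|---|
| 1.0 | 1.0 | 5% | 5% |
| 1.5 | 1.37 | 30% | 24% |
| 2.0 | 1.70 | 70% | 55% |
| 2.5 | 2.02 | 87% | 75% |

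The first row is the type I error, which is about 5% with either coding, so the gain does not come from extra false positives.

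**The case against.** **A linear term is not always better.** Continuous age holds more information than two groups, but the remedy is one linear term, which assumes a shape. The efficiency figure is a squared correlation and works both ways: if the true relation were a step at 60, the linear term would suffer the same 36–51% loss under the same age distributions. This stands. About 14 failures could not settle the shape, and a pre-stated cut-point does at least avoid one chosen from the data. Against that, the documents give no argument for a step at 60.

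**The practical gain is modest.** At an odds ratio of 1.5 per SD, age would usually be missed under either coding (30% versus 24% power). The plan also screens 12 candidate predictors on few failures, and recoding age does not cure that. Both points stand and keep this at the level of an improvement.

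**Stronger readings that the documents do not support.**

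- A reader might extend the point to alcohol, coffee and tea, which are also split ("history of alcohol consumption (<80 g/day or" at least 80 g/day; "ingestion of coffee (<1 cup/day or" and "ingestion of tea ((<1 cup/day or" at least one cup a day). The documents do not show that amounts are recorded; the form may ask only which group applies. Recorded amounts could also be skewed, so that a few heavy users drive a linear term.
- A reader might infer that the split leaves other predictors confounded by age. Whether age is adjusted for at all depends mainly on the significance screen, which recoding leaves in place, and the documents do not show that age is related to any other predictor.
- A reader might take the 36–51% loss as a property of this trial. It is conditional on an age distribution and an effect shape that the documents do not give.

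**Conclusion.** The point holds for age, in conditional form. The plan analyses age only in two groups although age in years is necessarily held. Given a roughly linear effect on the logit, a roughly normal age distribution and about 20–50% of patients aged 60 or over, the split loses about 36–51% of the information on age, when only about 14 failures (about 7 to 17, before unknowns counted as ITT failures) are expected. In the simulated case this costs about 6 to 15 percentage points of power (30% − 24% = 6; 70% − 55% = 15). It is a worthwhile minor improvement to the second aim, not an error that threatens the trial. The primary comparison of eradication rates is untouched.

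**What to change.** In the Statistical analysis section, state that age enters both the univariate and the multivariable predictor analyses as a continuous variable, with the odds ratio given per 10 years, and that the under-60 and 60-or-over groups are used for descriptive tables only. Make the change before outcome data are examined, so that the coding is not chosen by its result.

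The cost is one line of text; no new data or visits are needed. The small price is lower efficiency if the true effect is a step at 60.
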